96 to liraglutide or glargine with or without oral agents at hospital discharge.
97

98 **Endpoints:**

99 **Study Outcomes:**

100 The primary outcome of the study is to determine differences in HbA1c concentration at 26
101 weeks from discharge between liraglutide and glargine insulin therapy.
102

103 The secondary outcome is to compare differences between treatment groups in any of the
104 following measures during the 26 weeks following hospital discharge in patients with T2D:

- 105 • Self-measured blood glucose (SMBG) 7-point profiles
- 106 • Fasting and postprandial BG concentration
- 107 • Incidence rate and number of hypoglycemic events (<70 mg/dl) and severe hypoglycemic
108 events (<40 mg/dl).
- 109 • Percent of patients with 26 week HbA1c $<7.0\%$ and no hypoglycemia
- 110 • Percent of patients with 26 week HbA1c $<7.0\%$ and no weight gain
- 111 • Percent of patients with 12 week HbA1c $<7.0\%$ and no hypoglycemia
- 112 • Change in body weight and BMI

- 113 • Cardiovascular risk factors including changes in blood pressure, heart rate, and lipid
- 114 profile.
- 115 • Total daily dose of insulin
- 116 • Number of emergency room visits and hospital readmissions
- 117 • Acute renal failure during the 26-week follow-up defined as a clinical diagnosis of acute
- 118 renal failure with documented new-onset abnormal renal function (increment in
- 119 creatinine ≥ 0.5 mg/dL from baseline)

120
121

122 **Study type:**

123 The trial is a 26-week, randomized, open label-controlled two-armed, multi-center, multi-
124 national trial investigating the efficacy and safety of liraglutide versus glargine insulin in
125 medicine and surgical patients with T2D after hospital discharge.

126 We will recruit a total of 330 poorly controlled (HbA1c $\geq 7\%$ -10%) patients with T2D treated
127 with diet or oral antidiabetic agents (OAD) or on low-dose insulin therapy (TDD ≤ 0.4
128 unit/kg/day) prior to admission. Patients will be treated with a standard basal bolus insulin
129 regimen during the hospital stay. Prior to hospital discharge, patients will be randomized to
130 liraglutide or glargine with or without oral antidiabetic drugs. After discharge, a member of the
131 diabetes research team will contact patients via telephone call every 2 weeks to assess response
132 to therapy. In addition, patients will be asked to attend an outpatient clinic visit at 2 (optional), 4,

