133 12 and 26 weeks after hospital discharge. Recommendation on insulin dose adjustment will be
134 provided to patients at each telephone contact and clinic visits.

135
136 Recommendation for liraglutide dose escalation will be done every one or two weeks until the
137 maintenance dose of 1.8 mg is reached. Dose escalation can be extended over 2 weeks at the
138 discretion of the investigator in case of gastrointestinal adverse events. Liraglutide and insulin
139 will be add-on to the subject's pre-admission OAD regimen. Dose of OAD should remain
140 unchanged throughout the trial, however dose reduction of insulin and sulfonylurea is allowed
141 due to hypoglycemia.

142
143
144 **Study Groups:**

145 We plan to analyze a total of 280 patients (who receive study medication) with T2D at the time
146 of hospital discharge.

- 147
- 148 • Group 1. Liraglutide once daily in combination to OADs (n=140).
- 149
- 150 ▪ Group 2. Glargine once daily in combination to OADs (n=140).

151
152

153 **Study population:**

154 This will analyze 380 general medicine and surgical patients with a known history of T2D, age
155 18-80, treated with diet alone and/or oral antidiabetic agents including sulfonylureas, repaglinide,
156 nateglinide, DPP4s, SGLT2, or metformin as monotherapy or in combination therapy or on low-
157 dose insulin therapy (TDD ≤ 0.4 unit/kg/day) prior to admission. Subjects will be recruited from 5
158 medical centers in the United States. A total of 300 patients will be recruited at Grady Memorial
159 Hospital, Emory University Hospital and Emory Midtown hospital.

161 **Study Sites:** This study will be performed at Grady Memorial Hospital, Emory University
162 Hospital, Emory University Hospital at Midtown, and 3 institutions in the United States:

- 163 1. MetroHealth Medical Center, Cleveland (PI: [name].)
- 164 2. State University of NY at Buffalo (PI: [name].)
- 165 3. University of Miami, Florida (PI: [name].)
- 166 4. Sanatorio Guemes, Buenos Aires -Argentina (PI: [name])

169 **Inclusion Criteria**

- 170 1. Males or females between the ages of 18 and 80 years discharged after hospital admission
171 from non- ICU general medicine and surgical services (excluding gastrointestinal and
172 cardiac surgeries).
- 173 2. Admission HbA1c between 7% and 10%
- 174 3. Patients with T2D treated with diet alone or with oral antidiabetic agents as monotherapy or in

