6. Insulin administration (if needed).

Follow-up Care:

- If baseline visit was not fully completed at the time of discharge, patients will be scheduled to return for a short in-person visit to complete (body measurements) study procedures within 7 days of discharge. Research team will call to verify correct administration of study medication and availability of medications and glycemic control monitoring supplies.

- 300 • After discharge, a member of the diabetes research team will contact patients via
301 telephone call every 2 weeks for a total of 26 weeks.
- 302 • Patients will be asked to attend the next outpatient clinic visit at 4 weeks of hospital
303 discharge. During this visit, patients will receive 8 weeks drug supply of liraglutide and
304 will be asked to return to clinic at 12 weeks for the next outpatient visit. During this visit,
305 patients will receive 12 weeks (3 months) drug supply of liraglutide and will be asked to
306 return to a fourth and final visit at 26 weeks of hospital discharge.
- 307 • Recommendations on insulin adjustment will be provided to patients at each telephone
308 and clinic visits by a licensed physician (fellow or study physician) (see section Vf).

309 **During follow up we will collect the following information:**

- 310 1. Glycemic control:
- 311 a. Mean daily fasting and premeal blood glucose levels.
- 312 b. HbA1c at 3 and 6 months of discharge
- 313 c. Number of hypoglycemic events
- 314 - **Symptomatic hypoglycemia** is defined as an event with typical symptoms (i.e.,
315 sweating, palpitation, and feeling of hunger) with or without confirmation by
316 plasma glucose <70 mg/dl (3.9 mmol/L).
- 317 - **Severe hypoglycemia** is defined as episodes necessitating assistance and
318 associated with measured plasma glucose < 40 mg/dl (2.2 mmol/L) or with
319 prompt recovery after administration of carbohydrates, glucagon, or other
320 resuscitative actions. These episodes may be associated with sufficient
321 neuroglycopenia to induce seizure or coma. Blood glucose measurements may
322 not be available during such an event, but neurological recovery attributable to
323 the restoration of BG to normal is considered sufficient evidence that the event
324 was induced by low plasma glucose.
- 325
- 326 2. Diabetes treatment:
- 327 a. Number of patients receiving insulin therapy, dosage and compliance.
- 328 b. Use of liraglutide and other oral agents, dosage and compliance.

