- 329 c. Protocol adherence by PCP (diabetes clinic versus PCP)
- 330
- 331 3. Clinical Outcome:
- 332 a. Hospital readmissions
- 333 b. Emergency room visits
- 334
- 335
- 336

337 **7-point self-measured blood glucose profile:**

338 Subjects will be instructed to perform a 7-point SMBG profile three times during the trial within
339 one week prior to site visit on a day where the subject do not anticipate unusual strenuous
340 exercise.

341 **Time-points for 7-point profile:**

342
343 The blood glucose levels should be measured and recorded in the diary (including date, actual
344 clock time and blood glucose value) at the following time points, always starting with
345 measurement before breakfast.

- 346
- 347 • Before breakfast
- 348 • 90 min after the start of breakfast
- 349 • Before lunch
- 350 • 90 min after the start of lunch
- 351 • Before dinner
- 352 • 90 min after the start of dinner
- 353 • At bedtime
- 354
- 355

356 **Body measurements**

357 Body measurements consist of the parameters: Body weight, height, waist circumference, hip
358 circumference and BMI

359 **Body weight:** Body weight should be measured in kilogram or pound, without shoes and only
360 wearing light clothing.

361 **Height:** Height (without shoes) should be measured in centimeters or inches and recorded
362 without decimals.

363 **Waist and hip circumference:** The waist circumference is defined as the minimal abdominal
364 circumference located midway between the lower rib margin and the iliac crest. The hip
365 circumference is defined as the widest circumference around the buttocks. Three consecutive
366 measurements of waist and hip circumference should be taken and recorded. Mean values will
367 be used for result analysis. The waist and hip circumferences will be measured to the nearest 0.5
368 cm (0.2 inches) using a non-stretchable measuring tape.

369 The subject should be measured in a standing position with an empty bladder and wearing light
370 clothing with accessible waist and hip. The tape should touch skin, but not compress soft tissue
371 and twist in tape should be avoided. The subject should be asked to breathe normally and the
372 measurement should be taken when the subject is breathing out gently.

373 **Body Mass Index (BMI):** BMI will be calculated by the formula Body weight (Kg)/m².

374

375

376

377

378 **Assessment for Safety**

379
380
381
382
383
384
385
386
387
388
389
390
391
392
393
394
395
396
397
398
399
400
401
402
403
404

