429 patients treated with liraglutide. In subjects with suspected acute pancreatitis liraglutide and
430 other potentially suspect medicinal products should be discontinued until confirmatory tests have
431 been conducted and appropriate treatment initiated.

432
433
434

STATISTICAL CONSIDERATIONS:

435 This study is randomized multicenter, open-label controlled trial. The overall hypothesis is that
436 patients with T2D discharged on liraglutide and glargine will experience similar improvement in
437 glycemic control (HbA1c level at 26 weeks post-discharge). In addition, we anticipate that
438 compared to patients treated with insulin glargine, patients on liraglutide will experience lower
439 number of hypoglycemic events and less weight gain during follow-up.

440

441 **Sample Size and Power Calculations:** The primary endpoint in this study is glycemic control
442 measured by HbA1c at 26 weeks after discharge between treatment groups. To show the non-
443 inferiority of liraglutide to basal glargine insulin in terms of glycemic control, we set the
444 equivalence margin as 0.5%, from a view that an HbA1c difference < 0.5% is usually not
445 considered as clinically significant.

446 Based on preliminary discharge data, we assume the standard deviation of 26 week A1c is
447 bounded about 1.5%. We set the margin of equivalence as 0.5% and assume the true difference
448 between mean A1c is 0. A sample size of 124 for each treatment group would achieve 80%
449 power to reject the hypothesis that the mean HbA1c in patients treated with liraglutide is < 0.5%
450 more than that in patients treated with glargine based on a two-sample one-sided t test, with
451 alpha=0.05. Accounting for 10% attrition rate, we would need 140 patients per treatment group.
452 This leads to a final total sample size estimate of 280 patients that receive study medication.

453

454 The secondary outcome of major interest in this study is the difference in hypoglycemia (BG <70
455 mg/dl). Based on our preliminary discharge data, 30-40% of patients treated with basal insulin
456 will have at least one hypoglycemia episode. Assuming a hypoglycemia rate of 20-35% in the
457 insulin group in this study, given the sample size of 140 subjects per treatment group, based on a
458 two sided Fisher's exact test with alpha=0.05, we would have 80% power to detect an odds ratio
459 in hypoglycemia rate of 0.42 in liraglutide group (versus glargine group). In the following table,

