460 we give the estimated power under different assumed group differences in hypoglycemia rate,
461 represented by four hypothesized odds ratios.

462 Table: Estimated power with 140 subjects per group (before 10% attrition) and the anticipated
463 hypoglycemia rate of 35% in the insulin group based on two-sided Fisher's exact test with
464 alpha=0.05.
465

Odds Ratio	0.2	0.3	0.4	0.5
Power	>0.99	0.97	0.85	0.64

466
467 The above calculations show that we will have a good chance to achieve over 80% power for the
468 secondary outcome of hypoglycemia rate.
469

470
471

472 **Analysis of Primary Endpoint:**

473 The primary endpoint in this study is glycemic control measured by HbA1c concentration at 26
474 weeks post-discharge. We will first compare the primary outcome using two-sample t-tests (or
475 Wilcoxon tests) or one-way ANOVA, followed by multivariate linear regression to estimate and
476 test the difference between the two treatment groups while simultaneously accounting for other
477 potential confounders. Particularly, we will investigate center effect for the HbA1c outcome by
478 stratified univariate analysis or multivariate linear regression. Transformations will be applied if
479 normality violation is detected. Stepwise, backward, or forward model selection strategy will be
480 adopted to determine the variables to be included in the final model. Standard diagnostic and
481 model checking procedures will be applied to examine the fit of the developed models.
482

483 **Analysis of Secondary Endpoints:**

484 Secondary endpoints in this study include rate of hypoglycemia, number of hypoglycemia
485 events, change in body weight in kilograms, number of episodes of severe hyperglycemia,
486 complications and Emergency Room or hospital readmissions. For hypoglycemia outcomes, we
487 will first conduct nonparametric comparisons of the rate of hypoglycemia based on a two-sided
488 Chi-square test (or Fisher's exact test in the presence of low incidence rates), followed by the
489 Cochran-Mantel-Haenszel test which adjusts for the potential center effect. Univariate Poisson
490 regression (or Negative Binomial regression) will be performed to assess whether there is any
491 difference in the number of hypoglycemia events between the two treatment groups. We will
492 further conduct multivariate Logistic regression, Poisson regression (or negative binomial

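### The primary non-inferiority analysis does not separate week-26 HbA1c values obtained after off-protocol glucose-lowering therapy, permanent stop of study drug or withdrawal, and no supporting analysis is planned

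*Combined protocol and SAP*

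**What the plan says.** Under Sample Size and Power Calculations, the aim is to show the non-"inferiority of liraglutide to basal glargine insulin in terms of glycemic control, we set the" margin at 0.5%. The reason given is that a smaller HbA1c difference is usually not thought clinically important. Randomization and Blinding confirms that the trial is open label.

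Under Analysis of Primary Endpoint, "The primary endpoint in this study is glycemic control measured by HbA1c concentration at 26" weeks. The analysis is a two-sample t-test, Wilcoxon test or one-way ANOVA, then a linear regression with selected covariates. The only wording on who is analysed, under Study Groups, refers to 280 patients who receive study medication.

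Four other parts of the protocol bear on treatment changes:

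- **Background drugs.** Under Study type, oral drug doses are to stay "unchanged throughout the trial, however dose reduction of insulin and sulfonylurea is allowed" because of hypoglycemia. Concomitant Illnesses and Medications bars upward adjustment of metformin, sulfonylurea and pioglitazone.
- **Study drugs.** Liraglutide rises to a fixed maintenance dose. The glargine algorithm raises the dose when mean fasting glucose exceeds 140 mg/dL without hypoglycemia.
- **Persistent hyperglycemia.** Withdrawal Criteria removes a patient whose confirmatory fasting value exceeds 240 mg/dL with no treatable cause. No add-on step is described.
- **Data collected.** Follow-up Care lists "Number of patients receiving insulin therapy, dosage and compliance", the use of liraglutide and oral agents, and "Protocol adherence by PCP (diabetes clinic versus PCP"). The secondary outcomes include "Total daily dose of insulin". None of these enters the primary analysis.

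**The concern.** Run as written, the primary test would use whatever week-26 values are available. A value reached on the randomised drug would count the same as one reached after another clinician added a drug, or after study drug was stopped. Patients withdrawn for hyperglycemia may have no value at all.

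The protocol gives the arms unequal room to respond to poor control. Between roughly 140 and 240 mg/dL fasting, a glargine patient has a protocol dose increase, while a liraglutide patient at the maintenance dose has no drug step. In addition, Rationale for Study Population has patients previously on low-dose insulin receive the study drug as monotherapy, so those assigned to liraglutide would stop insulin. More off-protocol therapy in the liraglutide arm is therefore plausible. If it lowers HbA1c there, it narrows a true disadvantage, and in a non-inferiority trial that favours a positive conclusion. With one analysis and no supporting one, a reader could not tell whether the result depends on such values.

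**Working it through.** **Inputs from the protocol:** margin 0.5, SD 1.5, true difference 0 for planning, one-sided alpha 0.05, 80% power, 124 per group, 140 per group after 10% attrition.

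**Inputs assumed, because the documents give none:** a net excess of 5-15% of the liraglutide arm receiving added therapy, with an HbA1c effect of 0.5-1.0 points.

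**Step 1. The plan's own figure.** n = 2 × [1.5 × (1.645 + 0.842) / 0.5]² = 111.3, so 112 per group; the exact t calculation also gives 112. The stated 124 is not reproduced. At 124 the power is 83.5%, so the difference is on the conservative side and does not affect this point. 124 / 0.9 gives 138, close to the stated 140.

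**Step 2. Standard error.** Evaluable per arm: 140 × 0.9 = 126. SE = 1.5 × √(2/126) = 0.189.

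**Step 3. Shift in the difference.** Shift = net excess × effect. Smallest: 0.05 × 0.5 = 0.025. Largest: 0.15 × 1.0 = 0.15.

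**Step 4. False non-inferiority rate at a true difference of 0.5.** Rate = Φ(shift/0.189 − 1.645). A positive shift means more added therapy on liraglutide.

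| Example | Shift | Rate |
|---|---|---|
| 10% × 1.0, more on glargine | −0.10 | 1.5% |
| No net imbalance | 0 | 5.0% |
| 5% × 0.5 | 0.025 | 6.5% |
| 5% × 1.0 or 10% × 0.5 | 0.05 | 8.4% |
| 10% × 1.0 | 0.10 | 13.2% |
| 15% × 1.0 | 0.15 | 19.7% |

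These rates count as errors only if the question is the effect of the drug without added therapy.

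**Step 5. Withdrawal without any added drug.** Assume true means of 7.5 (glargine) and 8.0 (liraglutide), SD 1.5, and loss of everyone above a cut-off c. The completer mean is μ − 1.5 × φ(a)/Φ(a), with a = (c − μ)/1.5.

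- c = 9.5: 9.1% and 15.9% are lost, and the completer difference is 0.34.
- c = 11: 1.0% and 2.3% are lost, and the completer difference is 0.46.

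A true difference of 0.50 thus shrinks to 0.34-0.46 among completers. This also rests on assumed means and cut-offs.

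**The case against.** A reader might infer that the plan credits the randomised drug with HbA1c reached after added therapy, and so biases the trial toward success. The documents do not support that, for four reasons.

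- **Silence is not a rule.** The primary analysis text neither counts nor excludes such values.
- **Added therapy would be off-protocol and its frequency is unknown.** There is no rescue step, and confirmed severe hyperglycemia leads to withdrawal. Tracking primary care adherence does not show that primary care physicians add drugs. Nor is off-protocol treatment the only way a liraglutide patient can improve: the protocol also provides diabetes education and repeated compliance checks.
- **The direction is conditional.** It favours non-inferiority only with a net excess on liraglutide. Non-adherence alone can do the opposite: patients who stop liraglutide without replacement would raise HbA1c in that arm. The protocol cites nausea and vomiting in up to 14% on liraglutide 1.8 mg against 3.5% on placebo. That is neither a stopping rate nor a comparison with glargine, but it makes this route plausible.
- **Using every observed value can be legitimate.** For a comparison of discharge strategies whatever treatment follows, it answers the question asked.

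The plan also has other relevant information: the number of patients receiving insulin is collected, and episodes of severe hyperglycemia are a listed secondary endpoint.

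All of this stands, and it limits the claim to a gap of unknown direction. It does not close the gap. The plan never says which question it addresses, and it has no second analysis to show whether the conclusion depends on the answer.

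**Conclusion.** The point holds as a gap in the primary analysis, not as a demonstrated bias. The plan does not distinguish week-26 HbA1c obtained after off-protocol therapy, permanent stop or withdrawal, and it offers no per-protocol or supporting analysis. The unequal room for dose adjustment makes an excess of added therapy on liraglutide plausible, but no more than that.

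The 6.5-20% range illustrates what is at stake. It depends on the assumed excess and effect, on 126 evaluable per arm, on SD 1.5, and on asking about the drug without added therapy. With balanced added therapy the error rate stays at 5%, and with more on glargine it falls below 5%. The sponsor should fix this before outcome data are examined. Confidence is medium, because the frequency of treatment changes cannot be judged from the documents.

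**What to change.** 1. Keep the all-observed comparison and name it as the treatment-policy analysis. Collect week-26 HbA1c after stop of study drug or withdrawal where consent allows.
2. Prespecify one supporting analysis. Set HbA1c after the start of a non-study glucose-lowering drug to missing. Impute it from baseline and week-12 HbA1c and fasting glucose under a conservative assumption, such as the non-inferiority null, with liraglutide values drawn as if that arm were worse by the full 0.5 points.
3. After permanent stop of study drug, use the observed value if there is one, and otherwise the same conservative imputation. Do not impute from on-treatment values, which credits patients with a drug they no longer take. If 10% stop liraglutide and would be 1.0 point higher off it, that choice alone shrinks the difference by 0.10 × 1.0 = 0.10.
4. Call non-inferiority robust only if the upper confidence bound is below 0.5% in both analyses.
5. Record start dates of non-study glucose-lowering drugs and report the proportion starting one by arm. The flow chart lists drug compliance at each post-discharge contact but has no row for concomitant medication. The insulin-dose outcome can stay as a descriptive measure.

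The cost is a paragraph of statistical text, one extra analysis with somewhat lower precision, and the recording of start dates. HbA1c is scheduled only at baseline, week 12 and week 26, so a patient who changes therapy before week 12 has only the baseline HbA1c, plus any fasting glucose taken before the change, to impute from. That is a further reason for the conservative assumption. No clinical rescue rule is proposed.
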